## **B. Statistical Considerations**

### ***Sample Size Justification:***

Based on available data from a prior study examining platelet inhibition of non-opioid analgesics, 10 a PFA closure time  $\geq 173$  seconds can be used to classify platelet inhibition. Using the aforementioned data on epinephrine-induced PFA closure time, 10 we estimate that, before and after ketorolac exposure, 25% and 70% patients respectively would exhibit prolonged PFA closure times. With an alpha error of 0.05 and a beta error of 0.8, we estimated that a sample size of 14 patients per group would provide 80% power.

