**Endpoints:**

Primary outcome: Platelet Aggregometry (ADP-agonist) will be performed before (baseline obtained at completion of the case) and 10 min after IV dosing of study drugs. The timing of the post-dose blood draw was selected because the maximum concentration (Cmax) of IV ketorolac is  $2.9 \pm 1.8$  minutes and known platelet inhibition correlates closely with Cmax.

Secondary outcomes: Platelet Aggregometry (AA-agonist), Thromboelastographic indices (TEG), including R time, K time, alpha angle, and maximum amplitude, TEG platelet mapping MA for AA and ADP, Platelet phosphorylation (pDrp1), laboratory coagulation indices (PT, PTT, INR, fibrinogen). TEG will be performed using a Thromboelastography® 6S analyzer (Haemoscope Corp. Niles, IL), TEG will be performed before (baseline obtained pre-operatively) and platelet phosphorylation (pDrp1) will be performed by PlateletDiagnostics (Allston, MA). Relevant clinical data will also be collected, including: total estimated blood loss, total volume of intravenous fluid given during the intraoperative period.

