### ***Data Analysis:***

Data will be assessed for normality using Q-Q normality plots and the Kolmogorov-Smirnov test. Demographic, obstetric, and perioperative data will be presented as mean (SD) or median [interquartile range]. Between-group comparisons will be assessed using the unpaired t test and Mann-Whitney U test, where appropriate. Within-group before vs. after NSAID exposure changes will be assessed using the paired t test and Wilcoxon signed rank test, where appropriate. The percentage change from baseline for each Platelet Aggregometry, TEG, and lab parameter will also be calculated.

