## **C. Subject Selection**

*We will study 40 healthy (ASA 1 or 2) women between 18 and 40 years old with singleton term pregnancies undergoing elective, scheduled cesarean delivery with neuraxial anesthesia. Patients will be randomized to receive either IV ketorolac 30 mg (n=20) or normal saline (n=20) before platelet tests. Exclusion criteria are as follows: known allergy or contraindication to NSAIDs, significant medical or obstetrical disease, thrombocytopenia (platelet count  $< 100 \times 10^9/L$ ), history of inherited or acquired coagulation disorder, pre-existing treatment with any of the following drugs: aspirin, NSAIDs, opioids, anticoagulants, and anti-platelet agents.*

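### The only stated power is for a PFA closure-time endpoint the trial does not measure; power for the primary outcome, ADP aggregometry, is undocumented and the enrolled 20 per group is not derived

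*Combined protocol and SAP*

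**What the plan says.** Section B3.A, Endpoints, names the primary outcome: "Primary outcome: Platelet Aggregometry (ADP-agonist) will be performed before" dosing and again 10 minutes after it. No responder threshold is given for aggregometry.

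Section B3.B, Sample Size Justification, works with a different assay. A closure time of at least 173 "seconds can be used to classify platelet inhibition". The agonist behind the cited data is epinephrine: "Using the aforementioned data on epinephrine-induced PFA closure time". The rates assumed from that source are as follows: "we estimate that, before and after ketorolac exposure, 25% and 70% patients respectively would exhibit prolonged PFA closure times". The error rates are given as "With an alpha error of 0.05 and a beta error of 0.8". On that basis the section concludes: "we estimated that a sample size of 14 patients per group would provide 80% power".

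Section B3.B, Data Analysis, says: "Between-group comparisons will be assessed using the unpaired t test and Mann-Whitney U test, where appropriate". Within-group changes get a paired t or Wilcoxon signed rank test, and percentage change from baseline is also calculated. No test of proportions is listed.

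Section B3.C, Subject Selection, sets enrolment: "Patients will be randomized to receive either IV ketorolac 30 mg (n=20) or normal saline (n=20) before platelet tests". The Brief Study Protocol gives the same 20 and 20.

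**The concern.** The calculation and the trial differ in four respects:

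| | Sample Size Justification | Primary outcome and its analysis |
|---|---|---|
| Assay | PFA closure time | Platelet aggregometry |
| Agonist | Epinephrine | ADP |
| Scale | Binary, cut at 173 seconds | No cut-off; t or rank tests |
| Contrast | Before versus after ketorolac | Ketorolac versus placebo (B1) |

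PFA is absent from the primary and secondary outcomes (Endpoints), from the pre-operative and 10-minute panels (Brief Study Protocol) and from Data Analysis. Elsewhere it appears only as background in B2. As written, the trial cannot run the analysis that its 80% describes.

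B2 and B5 link the result to NSAID use alongside postpartum anticoagulation, so a null finding would carry weight. Readers would judge a non-significant ADP result against an 80% power that was never calculated for it.

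**Working it through.** **1. Reproduce the plan's figure.** Inputs from the Sample Size Justification: p1 = 0.25, p2 = 0.70, alpha 0.05, power 0.80. The plan's "With an alpha error of 0.05 and a beta error of 0.8" is read as power 0.80, because the same sentence goes on to claim 80% power; a literal beta of 0.8 would be 20% power.

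Two-group comparison, pooled normal approximation:

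n = [z_alpha × √(2·p̄·(1−p̄)) + z_power × √(p1(1−p1) + p2(1−p2))]² / (p2−p1)²

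Here p̄ = 0.475, the first root is √0.49875 = 0.7062, the second is √0.3975 = 0.6305, and (0.45)² = 0.2025.

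- One-sided: (1.645 × 0.7062 + 0.8416 × 0.6305)² / 0.2025 = 1.6923² / 0.2025 = 14.1, which rounds up to 15. Power at 14 is 79.6%.
- Two-sided: (1.960 × 0.7062 + 0.8416 × 0.6305)² / 0.2025 = 1.9148² / 0.2025 = 18.1, which rounds up to 19. Power at 14 is 68.3%.

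So 14 per group matches the one-sided version to within rounding. Other two-sided formulas need 16 (unpooled), 18 (arcsine) or 23 (continuity-corrected). Two-sided power at 14 is 76.1% unpooled and 51.7% by Fisher's exact test. A paired, two-sided McNemar approximation comes close (14.8, so 15) only if no patient moves from prolonged to normal, and its exact power at 14 is then 66.3%.

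At 20 per group, two-sided power for PFA would be about 84% (pooled) or 73.1% (Fisher). All these figures concern PFA only.

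**2. The step from 14 to 20.** Enrolment exceeds the calculated size by 6/14 = 43%. An allowance for unusable samples could explain it (14/20 = 70% evaluable), but no text says so.

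**3. What 20 per group gives for a continuous primary outcome.** The documents give no mean, SD or target difference for ADP aggregometry, so results are in SD units. Assumptions: unpaired t test, two-sided 0.05, noncentral t with df = 2n − 2 and noncentrality d × √(n/2).

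| True difference (SD) | Power, 20 per group | Power, 14 per group |
|---|---|---|
| 0.5 | 34% | 25% |
| 0.8 | 69% | 53% |
| 1.0 | 87% | 72% |
| 1.2 | 96% | 86% |

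The difference detectable with 80% power is 0.91 SD at 20 per group and 1.10 SD at 14. The half-width of the 95% CI at 20 per group is 2.024 × √(2/20) = 0.64 SD.

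**4. Dependence on the contrast.** Data Analysis does not say whether the post-dose value, the change or the percentage change is compared. With an assumed correlation r between baseline and post-dose values and equal SDs, 0.909 SD is multiplied by √(2(1−r)) for change scores and by about √(1−r²) for baseline adjustment:

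- Change scores: r = 0.3 gives 0.909 × 1.183 = 1.08 SD; r = 0.8 gives 0.909 × 0.632 = 0.57 SD.
- Baseline adjustment: r = 0.3 gives 0.909 × 0.954 = 0.87 SD; r = 0.8 gives 0.909 × 0.600 = 0.55 SD.

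The plan contains no covariate adjustment and no value of r.

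**The case against.** The strongest reply is that PFA stands in for platelet inhibition in general and that 20 per group leaves a margin over 14. If closure times were normal with equal SDs, a move from 25% to 70% beyond a fixed cut would be a shift of 0.674 + 0.524 = 1.20 SD. Were ADP aggregation to respond as strongly, 20 per group would give 96% power.

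That stands as a possibility and rules out calling the trial underpowered. A reader might infer low power from the 34% and 69% figures, but the documents equally allow differences at which power exceeds 80%. The argument does not rescue the stated power, however: the protocol offers no link between epinephrine-induced closure time and ADP aggregation, and the margin over 14 is a margin on another endpoint.

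A reader might also treat the before/after rates as a separate error. That would be too strong. Using the pre-drug rate for the placebo rate is a common simplification, and the figure is stated per group and reproduces as a two-group comparison. It needs only to be declared as an assumption.

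Nor does the whole sample size rest on PFA. Only the 14 and its 80% do; the 20 has no stated basis.

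**Conclusion.** The point holds. The plan's single power statement belongs to an assay, agonist, scale and test that the trial does not use, and power for ADP aggregometry is undocumented. Whether it lies above or below 80% cannot be determined from the documents. Even on its own endpoint, the figure of 14 needs a one-sided test that the plan does not declare.

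The 0.91 SD assumes an unpaired t test on the post-dose value, two-sided 0.05 and 20 evaluable patients per arm. It changes if the contrast is change from baseline or is baseline-adjusted. This should be corrected before the result is interpreted, because it is the only rationale offered for the only primary outcome.

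**What to change.** Remove the PFA calculation as the basis for power and replace it with a paragraph that:

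- states the sensitivity for ADP aggregometry at the fixed 20 per arm: 80% power for about 0.91 SD (unpaired t test, two-sided 0.05), with power at 0.5, 0.8, 1.0 and 1.2 SD;
- names the primary between-group contrast (post-dose value or change). The baseline draw must also be reconciled: Endpoints places it at the end of the case, the Brief Study Protocol before surgery;
- converts the SD units to assay units with a sourced aggregometry SD, and says whether that difference would matter;
- labels any change-score or baseline-adjusted figure as an assumption and shows it over a range of correlations;
- states sidedness, corrects the beta wording, and explains 14 versus 20.

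Add to Data Analysis that the between-group difference is reported with its 95% CI (half-width about 0.64 SD for the post-dose comparison), and that non-significance will not be read as absence of effect.

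The cost is a paragraph of protocol text and a source for the SD, with no extra patients. The downside is that the stated sensitivity may look less favourable than the present 80%.

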### ***Data Analysis:***

Data will be assessed for normality using Q-Q normality plots and the Kolmogorov-Smirnov test. Demographic, obstetric, and perioperative data will be presented as mean (SD) or median [interquartile range]. Between-group comparisons will be assessed using the unpaired t test and Mann-Whitney U test, where appropriate. Within-group before vs. after NSAID exposure changes will be assessed using the paired t test and Wilcoxon signed rank test, where appropriate. The percentage change from baseline for each Platelet Aggregometry, TEG, and lab parameter will also be calculated.

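### The between-group analysis names no tested variable and no baseline-adjusted model, although every patient has a baseline aggregometry; one ANCOVA should be prespecified, and it should gain power unless the baseline correlation is below about 0.2

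*Combined protocol and SAP*

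**What the plan says.** All of the analysis plan is one paragraph, Data Analysis, in section B3.B.

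- It opens with a normality check: "Data will be assessed for normality using Q-Q normality plots and the Kolmogorov-Smirnov test".
- It then gives the between-group rule: "Between-group comparisons will be assessed using the unpaired t test and Mann-Whitney U test, where appropriate".
- Changes within a group are tested with the paired t or Wilcoxon signed rank test.
- It closes: "The percentage change from baseline for each Platelet Aggregometry, TEG, and lab parameter will also be calculated". No test is attached to that quantity.

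No regression model or covariate appears, and no analysis is labelled primary.

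The baseline is planned in two places. For the primary measure, the Endpoints section states: "Platelet Aggregometry (ADP-agonist) will be performed before (baseline obtained at completion of the case) and 10 min after IV dosing of study drugs". By contrast, the Brief Study Protocol section places baseline aggregometry, with TEG, platelet mapping and pDrp1, before the operation on the day of surgery. It lists two study draws, one pre-operative and one 10 minutes after vial A.

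**The concern.** The hypothesis in section B1 is a comparison with placebo, so the between-group test carries the conclusion and the within-group tests cannot replace it. That test is left open in two ways: the variable is unnamed, and the choice between t and Mann-Whitney is made after looking at the data, with no stated rule for reading the Q-Q plots or for acting on the Kolmogorov-Smirnov result.

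Two things are at stake. One is room to choose among several analyses of the primary outcome. The other is efficiency: with 20 patients per arm, differences between patients that the baseline could explain stay in the error term if the test is applied to the post-dose value, and are only partly removed if it is applied to a change score.

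**Working it through.** **The plan's own figure.** The sample size section assumes that "before and after ketorolac exposure, 25% and 70% patients respectively would exhibit prolonged PFA closure times" and concludes that "a sample size of 14 patients per group would provide 80% power". With 25% against 70% and alpha 0.05, the pooled two-proportion formula gives 15 per group one-sided (79.6% power at 14) and 19 two-sided (68.3% at 14). So 14 is reproduced closely only as a one-sided calculation. It concerns a binary PFA closure time and supplies no SD, effect or correlation for aggregometry, so it cannot show the size of any gain here.

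**Inputs.**
- From the documents: 20 per arm (section C), alpha 0.05.
- Assumed: two-sided testing, normal data, equal SD before and after dosing, a true effect d = 0.8 SD, and a baseline-to-post correlation r from 0 to 0.7.

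**Formulas** (noncentral t; nc is the noncentrality parameter).
- Post-dose value only, 38 df: nc = d·√(n/2) = 0.8·√10 = 2.53; power 69.3%.
- Change score, 38 df: divide that nc by √(2(1−r)).
- ANCOVA, 37 df: divide it by √((1−r²)(1+1/36)). The factor 1+1/36 is the expected price of chance baseline imbalance with 40 patients.

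| Assumed r | ANCOVA variance factor (1−r²)·37/36 | ANCOVA power | Difference from 69.3% |
|---|---|---|---|
| 0 | 1.028 | 68.1% | −1.2 points |
| 0.2 | 0.987 | 69.9% | +0.6 |
| 0.3 | 0.935 | 72.2% | +2.9 |
| 0.5 | 0.771 | 80.1% | +10.8 |
| 0.7 | 0.524 | 92.5% | +23.2 |

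On variance alone, break-even is where (1−r²)·37/36 = 1, that is r = √(1/37) = 0.16. The lost degree of freedom moves it up very slightly, so it lies between 0.15 and 0.2.

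The change score has 69.3% power at r = 0.5 and 88.9% at r = 0.7, in both cases below ANCOVA.

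**Second anchor.** With an effect of 0.909 SD, at which the unadjusted t test has 80% power, ANCOVA gives 78.9% (r = 0), 82.5% (0.3), 89.0% (0.5) and 97.2% (0.7). Simulation of 20,000 trials per setting gave 78.6%, 83.2%, 89.2% and 97.0%, with ANCOVA type I error between 4.7% and 5.0%.

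**Cost of leaving the variable open.** Under no effect, with 20 per arm, normal data, an assumed baseline CV of 20% and r from 0.3 to 0.7, taking the smallest p from t tests on the post value, change and percentage change gives a false-positive rate of 9 to 10%. Adding the Mann-Whitney version of each gives about 11%. This is the worst case of free selection, but the plan's wording excludes none of these six tests.

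**The case against.** The strongest reply is that nothing here is an error. Unadjusted t and Mann-Whitney tests are valid in a randomized trial, and preferring ANCOVA is a choice about efficiency. That stands.

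A reader might also infer four stronger things that the documents do not support.

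- *That ANCOVA must raise power at no cost.* The correlation is not given, and a low one is plausible: if the baseline is pre-operative, surgery, blood loss and fluids come between the two samples. At r = 0 ANCOVA loses about 1 point.
- *That the plan ignores baseline in comparing groups.* Since the variable is unnamed, the test could be meant for change or percentage change, which do use baseline. What can be shown is ambiguity and the absence of an adjusted model.
- *That percentage change is badly inefficient.* This depends on an assumed CV. At d = 0.8 and r = 0.5, with a falling outcome, simulated power is about 70% at CV 20%, 61% at 30% and 46% at 40%. The low end comes from a normal model that allows near-zero or negative baselines; a strictly positive lognormal model at CV 40%, with a 0.8 SD effect on the log scale, gives 65 to 67%.
- *That the Kolmogorov-Smirnov test almost never rejects at n = 20.* That holds only without the Lilliefors correction, and the plan does not say which form is meant. Simulated rejection for normal, lognormal (sigma 0.5) and exponential data is about 0.01%, 1.5% and 4% uncorrected, but about 5%, 35% and 57 to 60% corrected. Q-Q plots are also listed.

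What remains is that the tested variable and the rule for choosing the test are not fixed in advance, and that a usually more efficient analysis of data already planned is not specified.

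**Conclusion.** The point holds in a limited form. The plan leaves the primary between-group analysis under-specified and plans no baseline-adjusted model despite a baseline for every patient.

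Under an assumed 0.8 SD effect at 20 per arm, ANCOVA moves power from 69% to between 68% (r = 0) and 93% (r = 0.7). The trade is lopsided: about 1 point lost at worst, against roughly 3, 11 or 23 points gained at r = 0.3, 0.5 or 0.7. The direction of the gain is firm above about r = 0.2; its size rests on an effect and a correlation that the documents do not state.

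The case for fixing one analysis does not depend on the correlation. The change should be made, but the trial would not be invalid without it.

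**What to change.** 1. Reconcile the Endpoints section (baseline at the end of the case) with the Brief Study Protocol section (baseline before the operation), and name one covariate shown to be drawn before vial A. The second section gives vial A during skin closure, so a sample at the end of the case needs its order relative to dosing stated.
2. Prespecify one primary analysis: a linear model (ANCOVA) of 10-minute ADP aggregation on arm and the named baseline, reporting the adjusted difference, 95% CI and two-sided p.
3. Use the same model for each secondary assay measured both before and after dosing.
4. Fix one rank-based sensitivity analysis, such as rank ANCOVA, and do not let a normality test choose the primary test.
5. Keep percentage change and the within-group tests descriptive.

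The analysis change costs wording and one degree of freedom, with no added patients. It needs no added blood draw if the pre-operative sample is the covariate. If the end-of-case sample is, the procedures must list a draw that they do not now contain.

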## **C. Subject Selection**

*We will study 40 healthy (ASA 1 or 2) women between 18 and 40 years old with singleton term pregnancies undergoing elective, scheduled cesarean delivery with neuraxial anesthesia. Patients will be randomized to receive either IV ketorolac 30 mg (n=20) or normal saline (n=20) before platelet tests. Exclusion criteria are as follows: known allergy or contraindication to NSAIDs, significant medical or obstetrical disease, thrombocytopenia (platelet count  $< 100 \times 10^9/L$ ), history of inherited or acquired coagulation disorder, pre-existing treatment with any of the following drugs: aspirin, NSAIDs, opioids, anticoagulants, and anti-platelet agents.*

**B4. POSSIBLE BENEFITS**

Patients in this study will obtain no direct benefits from participation in the study. Although randomization occurs, due to crossover dosing of patients after blood samples have been obtained, both groups will receive ketorolac for analgesia. This study seeks to better define the degree of platelet inhibition and any possible clinically significant effect for future patients, which may include these patients with subsequent pregnancies.

**B5. POSSIBLE RISKS AND ANALYSIS OF RISK/BENEFIT RATIO**

*This study poses no more than minimal risk to the patient population. Ketorolac and other non-steroidal anti-inflammatory drugs (NSAIDs) added to a post-cesarean analgesic regimen has been shown to improve the quality of post-cesarean analgesia and markedly reduce opioid consumption. They are routinely included in standard orders for many surgeries including cesarean section nationwide, as well as at this institution. The gained knowledge from this study will define the effect of ketorolac in this patient population, which has not been previously defined, and may be important given the new standard use of anticoagulation for at-risk post cesarean patients.*

**B6. RECRUITMENT AND CONSENT PROCEDURES****Recruitment**

Subjects will all be under the study investigators care and study investigators will recruit eligible patients in person during their labor and delivery visit with a physician.

**Consent**

Once a subject is deemed eligible and agrees to participation in the study, she will meet with a study investigator to begin the informed consent process. No consent will be obtained from patients needing urgent or stat Cesareans, as institutionally defined, in order to ensure that patient have enough time for the consent process and are not in an adverse emotional state at the time of consent. Informed consent will be documented by the use of a written consent form (attached). Each potential participant will have the opportunity to review the consent form with a physician co-investigator to discuss potential benefits and risks of participation. When all questions have been addressed, written consent will be officially obtained. For patients that request additional time to decide on participation, they will be provided with a phone number to call if they desire to proceed. Written informed consent can then be obtained at a subsequent time. All subjects will receive a copy of the signed consent form.

**Subject Protection**

*Consent will be obtained prior to routine, scheduled cesarean section at or around the time of general consent for the procedure. No consent will be obtained from patients needing urgent or stat Cesareans, as institutionally defined, in order to ensure that patient have*

*enough time for the consent process and are not in an adverse emotional state at the time of consent.*

## **B7. STUDY LOCATION**

### **Privacy**

Screening will occur during the normal pre-operative evaluation performed on Labor and Delivery prior to meeting the patient in the pre-operative holding area. Recruitment will be performed in the holding area per standard consent for patients for their cesarean section.

